4.3.2 Prohibited Therapy

The following medications are prohibited during the trial: 5-ASA products (oral or topical rectal), loperamide and other antidiarrheal agents, mucilages, antibiotics (metronidazole and ciprofloxacin), NSAIDs, nicotine patch, corticosteroids (oral, intravenous, intramuscular, or rectal), immunomodulating/suppressing drugs and biologics. Aspirin (except for cardioprotective reasons - maximum dose 325 mg/day) is prohibited during the trial.

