4.4 Withdrawal Criteria

Subjects have the right to withdraw from the trial at any time for any reason, without the need to justify their decision. However, the investigator should record the reason for the subject's withdrawal. The investigator also has the right to withdraw subjects.

Subjects will be withdrawn in the following cases:

- pregnancy at any time during the trial will be a reason for withdrawal
- withdrawal of consent
- worsening of UC with a need for an escalation of the therapy (i.e., surgical therapy, use of steroids, immunosuppressive or immunomodulating drugs, biologics, increase dose of 5-ASA in any form)
- request for termination of the trial by regulatory authorities or sponsor
- the subject develops any AE that, in the opinion of the investigator, warrants the subject's withdrawal from treatment. An AE form will be completed as appropriate, and the subject will be followed until the event is clinically stable.

For subjects who discontinue due to an AE, all efforts will be made to follow the outcome of the AE and to assess the efficacy criteria.

For any discontinuation, the investigator will obtain all the required details and document the date of the premature termination and the main reason in the electronic case report form (eCRF). Since an excessive rate of withdrawals can render the trial devoid of meaning, the unnecessary withdrawal of subjects should be avoided.

Subjects who withdrew from the trial will not be replaced.

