3.2 Determination of Sample Size

The true remission rates at Month 6 for mesalamine 2 g extended release granules (sachet) and placebo regimens were assumed as 68% and 49%, respectively, based on The mesalamine Study Group (1996)(3), Hawkey et al (1997)(4), and Apriso™ package insert (2009)(5). Under these assumptions, a sample size of 120 randomized subjects per group will provide at least 85% power to detect a statistically significant treatment group difference in the remission rate at a two-sided 0.05 significance level using the chi-square test. To maintain the power for the primary efficacy analysis that excludes subjects who are rolled over from the placebo group in the 000174 trial via Pathway 1, approximately 260 subjects will be randomized.

4 Subject Disposition

The number of screened subjects will be summarized, and for subjects not randomized, the primary reason for exclusion from randomization will be summarized.

The number and percentage of subjects who are randomized, are treated with IMP, prematurely discontinued, and completed the trial will be summarized with the reason of premature discontinuations.

The time to discontinuation will be summarized by the Kaplan-Meier estimates, and the treatment group difference will be tested by the log-rank test. In addition, reason-specific discontinuation will be summarized by the cumulative incidence estimates.

5 Protocol Deviations

The following protocol deviations will be identified as major protocol deviations:

- Overall IMP compliance of less than 80%
- Not taking the randomized IMP
- Taking prohibited medications

The final definition of major protocol deviations will be determined prior to breaking the blind.

The number and percentage of subjects with protocol deviations will be summarized.

6 Analysis sets

For each analysis set, the number and percentage of subjects excluded from it will be summarized by the reason of the exclusion.

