6.4 Per Protocol Analysis Set

The Per-protocol (PP) analysis set includes all subjects who receive at least one dose of IMP and who do not have any of the major protocol deviations defined in Section 5 in the ITT analysis set.

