9.2 Primary Endpoint(s)

9.2.1 Primary Variable(s) Analysis

The primary efficacy analysis will be based on the ITT analysis set. The proportion of subjects in remission, defined as rectal bleeding of 0 and stool frequency scores of 0 or 1 with an endoscopic score of 0 or 1 in the Clinical and Endoscopic Response Score at Month 6, will be assessed by the Mantel-Haenszel test stratified by the randomization strata at a two-sided 0.05 significance level. Subjects who discontinue the double-blind regimen before Month 6, as well as subjects with missing remission assessment at Month 6, will be considered not having met the remission criteria. The common odds ratio will be estimated using the Mantel-Haenszel adjusted odds ratio estimate, and its 95% confidence interval will be provided. The homogeneity of odds ratios across the randomization strata will be tested by the Breslow-Day test at a 0.05 significance level, and the odds ratio for each stratum will be presented in forest plots. The quantitative or qualitative nature of the possible treatment by stratum interaction will be assessed and discussed.

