9.2.2 Sensitivity Analyses

The following sensitivity analyses will be conducted to assess the robustness of the primary analysis:

- As-treated analysis based on actually received treatment
- Analysis on the all randomized analysis set
- Analysis on the mITT analysis set
- Analysis on the PP analysis set
- Analysis using the last observed Clinical and Endoscopic Response Score

The same analysis conducted for the primary analysis will be repeated for these sensitivity analyses.

Since the definition of remission was modified during the study, an analysis based on the original definition, i.e., rectal bleeding and stool frequency scores of 0 with an endoscopic score of 0 or 1 in the Clinical and Endoscopic Response Score, will also be conducted for reporting purpose.

In addition, sensitivity analyses using multiple imputation (MI) methods and pattern mixture models (PMMs) under missing at random (MAR) and missing not at random (MNAR) assumptions, respectively, will be conducted.

Under the MAR assumption, the missing stool frequency and rectal bleeding scores (Clinical Response scores) for Months 2, 4, and 6 will be imputed sequentially by regression-based imputation models using treatment group, baseline characteristics, and outcomes from preceding visits as the predictors. Once the missing Month 6 Clinical Response scores have been imputed, Month 6 Endoscopic Response score will be imputed by regression-based imputation models using treatment group, baseline characteristics, and Month 6 Clinical Response scores as the predictors. Based on the imputed Clinical and Endoscopic Response scores, the remission status at Month 6 will be determined. This imputation procedure will be repeated 100 times, and the primary analysis method will be applied to each of the imputed dataset. A combined estimate of the odds ratio for the treatment group compared to the control group and its 95% confidence interval will be obtained by the methods described in Rubin (1987)(6) .

Under the MNAR assumption, a similar MI method described above will be applied. However, in this analysis, only the data from the control group will be used for the regression-based imputation for Clinical Response scores at each visit and Endoscopic Response score at Month 6 by assuming that subjects from the treatment group will follow the same profile as the subjects on the control group after withdrawal from the study (Little & Yau, 1996(7); Ratitch & O’Kelly, 2011(8)).

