9.3 Secondary Endpoint(s)

The following key secondary endpoints will be analyzed for the ITT analysis set.

- The proportion of subjects in clinical remission at Months 2, 4, and 6, defined as a score of 0 for both rectal bleeding and stool frequency based on Clinical Response Score subset of the Clinical and Endoscopic Response Score
- Time to relapse, defined as number of days from randomization to the day of withdrawal due to escalation of therapy (i.e., surgical therapy, use of steroids, immunosuppressive or immunomodulating drugs, biologics, increase dose of 5 ASA in any form)

- The proportion of subjects with an increase from baseline in the Clinical and Endoscopic Response Score by 2 or more points in at least 1 component or by 1 or more points in at least 2 components at Month 6
- The change from baseline in serum CRP levels at Months 2, 4, and 6
- The change from baseline in fecal calprotectin levels at Months 2, 4, and 6

The proportion of subjects in clinical remission at Months 2, 4, and 6 will be analyzed by the generalized estimating equations (GEE) approach as longitudinal binary outcomes. The model will include the randomization strata, treatment, time, and treatment- by-time interaction. The clinical remission rates and odds ratio will be estimated for each time point. The overall treatment difference over 6 months will be estimated as the main effect for treatment in the model. The missing values will be imputed as non-remission, and an unstructured working correlation matrix will be used.

The time to relapse will be analyzed by the log-rank test stratified by the randomization strata. If a subject does not have the relapse by Day 168, the time to relapse will be censored at the earlier of the day that the last visit day or Day 168. The hazard ratio of relapse for mesalamine relative to placebo will be estimated (including the 95% CI) using the stratified Cox proportional hazards model with treatment group as a factor and the randomization strata as a stratification variable.

The proportion of subjects with an increase from baseline in the Clinical and Endoscopic Response Score by 2 or more points in at least 1 component or by 1 or more points in at least 2 components at Month 6 will be analyzed using the same statistical method used for the primary efficacy analysis.

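### The per-protocol set can drop subjects for taking the drugs whose use for worsening UC marks treatment failure (minor; PP sensitivity analysis only)

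*SAP*

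**What the plan says.** SAP Section 5 names three major protocol deviations, one of which is "Taking prohibited medications". Protocol 9.3 carries the same item. Neither states an exception. SAP 6.4 restricts PP to treated ITT subjects "who do not have any of the major protocol deviations defined in Section 5".

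Protocol 4.3.2 lists what is prohibited during the trial. The list includes every oral or rectal 5-ASA product and "corticosteroids (oral, intravenous, intramuscular, or rectal), immunomodulating/suppressing drugs and biologics". Protocol 4.4 requires withdrawal for "worsening of UC with a need for an escalation of the therapy" and gives surgery, the same drug classes and a higher 5-ASA dose as the forms of escalation. The relapse event in SAP 9.3 is "withdrawal due to escalation of therapy (i.e., surgical therapy, use of steroids, immunosuppressive or immunomodulating drugs, biologics" or an increased 5-ASA dose.

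For the primary endpoint, SAP 9.2.1 provides that "Subjects who discontinue the double-blind regimen before Month 6" count as not in remission. PP is one of the robustness analyses in SAP 9.2.2, which adds: "The same analysis conducted for the primary analysis will be repeated for these sensitivity analyses".

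**The concern.** Read together, these rules can treat one event in two ways. A subject whose UC worsens and who starts, say, a steroid before leaving the trial is a failure under the primary rule. The same steroid is a prohibited medication, so the deviation rule can delete that failure from PP.

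This is exclusion on outcome, not on adherence to the protocol. If the share of failures removed differs between arms, the PP odds ratio moves for reasons unrelated to treatment effect, and PP becomes harder to read as a check on the ITT result.

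**Working it through.** **Step 1: which failures the rule can reach**

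| Type of failure | Removed from PP by the prohibited-drug rule? |
|---|---|
| Escalation drug started for worsening UC while still in the trial | Can be |
| Withdrawn on a need for escalation, drug started only after participation ends | Not caught |
| Escalation by surgery alone | Not caught; surgery is not a medication |
| Stays on treatment, fails the Month 6 score | Not caught |

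Only the first row is at issue. The flow-chart note in Protocol 6.1 has discontinued subjects complete end-of-treatment assessments, so a drug could be started before the last visit. Nothing says how often that would happen.

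**Step 2: the plan's own figure**

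Inputs from SAP 3.2: remission 68% and 49%, 120 per group, two-sided 0.05, chi-square test, at least 85% power. With the pooled rate 0.585:

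- SE under the null = √(2 × 0.585 × 0.415 / 120) = 0.0636
- SE under the alternative = √((0.68 × 0.32 + 0.49 × 0.51) / 120) = 0.0624
- z = (0.19 − 1.96 × 0.0636) / 0.0624 = 1.05, so power = 85.2%

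The stated figure is reproduced. It serves here only to fix the planning inputs.

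**Step 3: illustration of the effect on PP**

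- Odds ratio at plan = (0.68/0.32) / (0.49/0.51) = 2.212
- Expected remitters = 120 × 0.68 = 81.6 and 120 × 0.49 = 58.8
- Expected non-remitters = 120 × 0.32 = 38.4 and 120 × 0.51 = 61.2

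Let f be the share of non-remitters removed from an arm. Remitters are untouched, so:

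- PP rate = remitters / (120 − f × non-remitters)
- PP odds ratio = 2.212 × (1 − f placebo) / (1 − f mesalamine)

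Every f below is an assumption. Differences use unrounded rates, and the odds ratio is unstratified.

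| f, mesalamine/placebo | Subjects removed | PP rates | Difference (points) | Odds ratio |
|---|---|---|---|---|
| 0/0% | 0 / 0 | 68.0% / 49.0% | 19.0 | 2.21 |
| 10/10% | 3.8 / 6.1 | 70.2% / 51.6% | 18.6 | 2.21 |
| 25/25% | 9.6 / 15.3 | 73.9% / 56.2% | 17.8 | 2.21 |
| 10/20% | 3.8 / 12.2 | 70.2% / 54.6% | 15.7 | 1.97 |
| 20/10% | 7.7 / 6.1 | 72.6% / 51.6% | 21.0 | 2.49 |

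Equal shares leave the odds ratio alone, though both rates rise and the difference shrinks. Equal headcounts are not equal shares: six removed per arm gives f = 6/38.4 = 15.6% and 6/61.2 = 9.8%, and an odds ratio of 2.212 × 0.902 / 0.844 = 2.36.

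**The case against.** The strongest reply is that the rule may catch few or none of these subjects. Protocol 3.5.7 and 4.4 tie withdrawal to a need for escalation, not to the first dose of the new drug. Protocol 4.3.2 prohibits drugs during the trial, and Protocol 3.5.8 hands subjects to local care with no further follow-up once participation ends. A subject withdrawn on need who starts a steroid afterwards has broken no rule. This stands. It limits the finding to drugs started while the subject is still in the trial and lowers confidence to moderate.

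Second, SAP Section 5 and Protocol 9.3 leave the final deviation definition to a decision before unblinding, and Protocol 9.4 does the same for assignment to analysis sets. Blinded review could settle the matter. But these clauses say when the decision is taken, not what it is, so they provide the occasion for the fix without making it.

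Third, the damage is contained. The primary analysis is on ITT, relapse is analysed on ITT, no decision rule rests on PP, and exclusions are tabulated by reason. All true, and why the point is minor. A tabulation makes the loss visible but does not put the failures back into the PP odds ratio.

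Fourth, subjects on prohibited drugs usually belong outside PP because the drug may confound the outcome. That holds for most of the list. It does not hold for a subject withdrawn for escalation, who is already a non-remitter and cannot be turned into a false remission by the drug.

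A reader might infer that PP will lose its relapses wholesale, or that the exclusion favours mesalamine. The documents support neither. They give no escalation or withdrawal rate, and the direction depends entirely on which arm loses the larger share.

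**Conclusion.** The gap is real and minor, and the correction is a cheap improvement. As written, the deviation rule can remove from PP a subject whom the plan itself counts as a treatment failure, because of the drug given for that failure. Confidence is moderate: the wording permits the exclusion, but whether it occurs depends on when the drug starts relative to the end of participation.

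The effect cannot be sized from the documents. Odds ratios of 1.97 and 2.49 against 2.21 show sensitivity to assumed unequal removal; they are not forecasts. ITT, mITT and all-randomized results do not exclude for deviations and are unaffected.

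**What to change.** When the deviation definition and the analysis-set assignments are finalised before unblinding, replace the item in SAP Section 5 with:

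*Taking prohibited medications, except an escalation drug listed in Protocol 4.4 started for worsening of UC that led to withdrawal; these subjects stay in PP, unless another major deviation applies, as non-remitters under SAP 9.2.1.*

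All other prohibited drugs, including antidiarrheals, remain deviations. This changes an analysis-set rule only, not what subjects may take or when they are withdrawn.

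The cost is one sentence and some blinded review. For any discontinuation the investigator must "document the date of the premature termination and the main reason in the electronic case report form", and Protocol 8.2.2 sends drugs given for an adverse event to the concomitant medication log. The documents do not say that a reason is recorded for every drug, so drug and start date must be matched to the withdrawal reason by hand while still blinded. The downside is that PP will then contain some subjects with prohibited drug use, which the report should state.

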6.1 All Randomized Analysis Set

The all randomized analysis set includes all randomized subjects. Analyses for the all randomized analysis set will be conducted according to the randomized treatment regardless of the actual treatment received.

6.2 Intention-To-Treat Analysis Set

The intention-to-treat (ITT) analysis set includes all randomized subjects who were assigned to mesalamine 4 g extended release granules in the 000174 trial or randomized via Pathways 2 or 3. Analyses for the ITT analysis set will be conducted according to the randomized treatment regardless of the actual treatment received.

6.3 Modified ITT Analysis Set

The modified ITT (mITT) analysis set includes all subjects who receive at least 1 dose of IMP in the ITT analysis set. Analyses for the mITT analysis set will be conducted according to the randomized treatment regardless of the actual treatment received.

6.4 Per Protocol Analysis Set

The Per-protocol (PP) analysis set includes all subjects who receive at least one dose of IMP and who do not have any of the major protocol deviations defined in Section 5 in the ITT analysis set.

6.5 Safety Analysis Set

The safety analysis set includes all subjects who receive at least one dose of IMP. Safety analyses will be conducted according to the treatment actually received.

7 Trial population

7.1 Demographics and Other Baseline Characteristics

Descriptive statistics of demographics and other baseline characteristics will be presented for all subjects in the ITT, PP, and safety analysis sets by treatment group unless otherwise specified.

Categorical data will be summarized using numbers and percentages. The percentages will be based on the total number of subjects with a corresponding assessment. Continuous data will be presented using the number of subjects, mean, standard deviation, median, minimum, and maximum.

7.1.1 Demographics

Baseline demographics and other baseline characteristics will be summarized by treatment group.

7.1.2 Disease Characteristics

Baseline disease characteristics (e.g., time since diagnosis of UC, extent of disease) will be summarized by treatment group.

Baseline Clinical and Endoscopic Response Scores will be summarized by treatment group.

7.1.3 Laboratory Efficacy/Pharmacodynamic Parameters at Baseline

Baseline serum CRP and fecal calprotectin levels will be summarized by treatment group.

7.2 Medical History

Medical history will be coded by system organ class (SOC) and preferred term (PT) using the Medical Dictionary for Regulatory Activities (MedDRA) version 17.1 or later and summarized by SOC (in alphabetical order), PT (in decreasing order of frequency), and treatment group for the ITT and Safety analysis sets.

7.3 Prior and Concomitant Medication

Prior and concomitant medications will be coded by the Anatomical Therapeutic Chemical (ATC) classification system and preferred drug name using the World Health Organization Drug Dictionary (WHO-Drug).

Prior and concomitant drug usage will be summarized by ATC classification 1st level (alphabetically), ATC classification 2nd level (in decreasing order of frequency) and treatment group for subjects in the ITT and Safety analysis sets. These medications will be tabulated separately for:

- 1) Prior medication; i.e. medication taken exclusively prior to treatment (i.e. with stop date before date of first IMP administration);
- 2) Concomitant medication, i.e. medication taken during the treatment period (i.e. medication that was not stopped before date of first IMP administration or started on or after the first IMP administration)

If the timing of the dose of a concomitant medication cannot be established in relation to the administration of IMP, it will be considered as concomitant medication.

7.4 Physical Examination

Subjects with abnormalities at any screening, baseline, or post-baseline visit will be listed with all physical examination evaluations.

8 Exposure and Treatment Compliance

8.1 Extent of Exposure

The length of the treatment, calculated as (last dose date – first dose date + 1), will be summarized by treatment group for the safety analysis set.

Following categorical summaries will be made:

- < 14 days, 14 - < 28 days, 28 - <56 days, 56 - <84 days, 84 - <112 days, 112 - <140 days, 140 - <168 days, and 168 days or more
- At least 1 day, at least 14 days, at least 28 days, at least 56 days, at least 84 days, at least 112 days, at least 140 days, and at least 168 days

8.2 Treatment Compliance

The overall compliance will be calculated as number of days with IMP intake based on the daily diary data divided by the number of days that the subject is supposed to take the IMP during the treatment period. It will be summarized for the safety analysis set.

9 Efficacy

9.1 General Considerations

All statistical tests will be conducted at a two-sided 0.05 significance level.

All secondary endpoints will be tested without adjustment for multiplicity.

Randomization strata will be included in stratified analyses for efficacy endpoints. For the ITT, mITT, and PP analysis sets, randomization strata will be defined as follows:

- Stratum 1: Pathway 1 (mesalamine 4 g extended release granules arm in the 000174 trial)
- Stratum 2: Pathway 2
- Stratum 3: Pathway 3

Randomization strata for the all randomized analysis set will be defined as follows:

- Stratum 1: Pathway 1a (placebo arm in the 000174 trial)
- Stratum 2: Pathway 1b (mesalamine 4 g extended release granules arm in the 000174 trial)
- Stratum 3: Pathway 2
- Stratum 4: Pathway 3

Stool frequency and rectal bleeding scores at each visit will be calculated as an average of the daily scores collected within 5 days prior to the visit (excluding the visit day and the day before the visit day if the bowel preparation is needed on the day before the visit). If the daily scores in this period are available for fewer than 3 days, the average score will be considered missing. The average scores will be rounded to the nearest integer for the final score determination (e.g., 0.3 will be rounded to 0, and 0.5 will be rounded to 1). Handling of missing data in the statistical analyses will be described for each endpoint.

For the endoscopic assessment, the outcomes determined by the independent central reading procedure will be used for all analyses.

For visit-based data, the data collected on the day that is closest to the scheduled trial day within a window will be assigned to the corresponding analysis visit. [Table 2](#) shows the scheduled trial day and window for each analysis visit.

Table 2 Scheduled trial day and window for analysis visits

Analysis visit	Scheduled trial day	Window
Baseline	Day 1	prior to the first dose of IMP

Analysis visit	Scheduled trial day	Window
Week 2	Day 14	Day 1 to Day 35
Month 2	Day 56	Day 36 to Day 84
Month 4	Day 112	Day 85 to Day 140
Month 6	Day 168	Day 141 or after

If the closest day cannot be uniquely identified for an analysis visit, the data collected on an earlier trial day will be assigned to the analysis visit.

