The change from baseline in serum CRP levels and fecal calprotectin levels at Months 2, 4, and 6 will be analyzed by repeated-measures analysis of covariance (ANCOVA) models that include the randomization strata, treatment, time, and treatment-by-time interaction as fixed effects, and the corresponding baseline value as a covariate. The adjusted changes from baseline and their difference between treatment groups will be estimated for each time point. The overall treatment difference over 6 months will be estimated as the main effect for treatment in the model. The missing values will be left as missing, and an unstructured correlation matrix will be assumed.

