9.4 Other Endpoint(s)

9.4.1 Health Related Quality of Life

The change from baseline in the IBDQ will be analyzed for the ITT analysis set.

The following domain scores for the IBDQ (Guyatt et al., 1989)(9) will be calculated by adding up scores from questions included in the domain for each subject at each time point:

- Bowel symptoms: Questions 1, 5, 9, 13, 17, 20, 22, 24, 26, 29
- Emotion function: Questions 3, 7, 11, 15, 19, 21, 23, 25, 27, 30, 31, 32

- Systemic symptoms: Questions 2, 6, 10, 14, 18
- Social function: Questions 4, 8, 12, 16, 28

The total score will be calculated by adding up all scores for each subject at each time point.

The handling of missing score in the calculation of the domain and total scores will be based on McMaster University (2010)(10). If there is only one missing response within a domain, the missing response will be imputed as an average of other responses within the domain. If there are two or more missing responses within a domain, the domain score will be considered missing.

If there are up to four missing responses, the missing responses will be imputed as an average of other responses. If there are more than four missing responses, the total score will be considered missing.

The change from baseline in the IBDQ domain and total scores at Months 2, 4, and 6 will be analyzed by repeated-measures ANCOVA models that include treatment, randomization strata, time, and treatment-by-time interaction as fixed effects, and the corresponding baseline value as a covariate. The adjusted changes from baseline and their difference between treatment groups will be estimated for each time point. The missing values will be left as missing, and an unstructured correlation matrix will be assumed.

10 Safety

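### The five key secondary endpoints are each tested at two-sided 0.05 with no adjustment, no order and no gate on the primary, so their p-values can only be nominal; a gated sequence would fix this cheaply

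*SAP*

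**What the plan says.** SAP 9.1 fixes one level for everything: "All statistical tests will be conducted at a two-sided 0.05 significance level". Protocol 9.6.1 says the same and does not mention multiplicity. SAP 9.1 then adds: "All secondary endpoints will be tested without adjustment for multiplicity".

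SAP 9.3 introduces a label that the protocol's endpoint lists do not use: "The following key secondary endpoints will be analyzed for the ITT analysis set". Five endpoints follow: clinical remission at three visits, time to relapse, worsening of the combined score at Month 6, change in CRP, and change in fecal calprotectin. For clinical remission, SAP 9.3 estimates rates and an odds ratio at each visit, plus an overall treatment effect. For the two biomarkers it says "The adjusted changes from baseline and their difference between treatment groups will be estimated for each time point", again with an overall effect. Time to relapse has one stratified log-rank test, and worsening has one Mantel-Haenszel test.

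The quality-of-life questionnaire is analysed under SAP 9.4, headed as other endpoints, and covers "The change from baseline in the IBDQ domain and total scores at Months 2, 4, and 6". SAP 2.2.2 lists its domain scores among the secondary endpoints but does not name the total score.

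**The concern.** Calling an endpoint key secondary in a Phase 3 efficacy trial invites readers to treat a significant result as more than exploratory. The plan gives that reading no support. A key secondary endpoint could reach p < 0.05 after the primary has failed, and nothing in the SAP says how that would be described. For clinical remission, CRP and calprotectin, SAP 9.1 says the endpoint is tested, but SAP 9.3 does not say which of four estimates is the test. That choice stays open until after the data are seen. What is at stake is the standing of the secondary results: without a controlled error rate, none of them can be more than nominal.

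**Working it through.** **1. The plan's own figure.** SAP 3.2 assumes Month 6 remission rates that "were assumed as 68% and 49%, respectively", and says "a sample size of 120 randomized subjects per group will provide at least 85% power". The pooled chi-square test without continuity correction uses a mean rate of (0.68 + 0.49)/2 = 0.585:

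- null SD term: √(2 × 0.585 × 0.415) = 0.697
- alternative SD term: √(0.68 × 0.32 + 0.49 × 0.51) = 0.684
- z = (0.19 × √120 − 1.96 × 0.697) / 0.684 = 1.05
- power = Φ(1.05) = 85.2%

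The stated figure reproduces. It concerns one primary endpoint with one test, so the secondary rule does not touch it. The documents give no familywise error rate and no count of secondary tests.

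**2. Counting contrasts** (SAP 9.3 and 9.4.1).

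| Endpoint | Contrasts |
|---|---|
| Clinical remission | 3 months + 1 overall = 4 |
| Time to relapse | 1 |
| Worsening at Month 6 | 1 |
| CRP change | 3 + 1 = 4 |
| Calprotectin change | 3 + 1 = 4 |
| **Key secondary, upper count** | **14** |
| IBDQ, 4 domains + total, 3 months | 5 × 3 = 15 |
| **With IBDQ** | **29** |

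The narrowest reading is one test per key endpoint, which gives 5. Leaving out the three overall effects gives 14 − 3 = 11. Using the IBDQ domains only, as in SAP 2.2.2, gives 14 + 4 × 3 = 26.

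**3. Chance of at least one false positive when no effect exists.** For k independent tests it is 1 − 0.95^k:

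- k = 5: 1 − 0.774 = 22.6%
- k = 11: 43.1%
- k = 14: 1 − 0.488 = 51.2%
- k = 26: 73.7%
- k = 29: 1 − 0.226 = 77.4%

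The expected number of false positives is 0.05k whatever the correlation: 0.25 for 5, 0.70 for 14 and 1.45 for 29.

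**4. Correlated tests.** The documents give no correlations, so these are assumptions. Test statistics were simulated as normal with a common correlation ρ (200,000 runs), counting runs with any |Z| > 1.96.

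| k | ρ = 0.3 | ρ = 0.5 | ρ = 0.7 | ρ = 0.9 |
|---|---|---|---|---|
| 5 | 20.8% | 18.3% | 14.9% | 10.1% |
| 14 | 43.9% | 34.7% | 24.8% | 14.2% |
| 29 | 65.2% | 50.1% | 33.5% | 17.1% |

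A block structure, with higher correlation within an endpoint than between endpoints, gives similar values. With 0.5 within and 0.1 between, 14 contrasts give 45.1%; with 0.7 and 0.3 they give 37.2%. Every scenario exceeds 5%, and the lowest is 10.1%.

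**5. Effect of a gate.** In a fixed sequence, each hypothesis is tested at 0.05 only if all earlier ones were rejected. A false rejection anywhere therefore requires rejecting the first true null in the order, which has probability at most 0.05. The familywise rate for the primary plus five key endpoints is then at most 5%, and the primary still uses its full 0.05.

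**The case against.** The case for leaving the plan alone is respectable. The SAP states openly that it makes no adjustment. The objectives separate the roles: the primary is there to demonstrate efficacy, and the secondary objectives use the language of evaluating and assessing. No section assigns a confirmatory or labelling claim to a secondary endpoint. The word key carries little weight, since it covers every secondary efficacy endpoint except the IBDQ. All of this stands, and it keeps the point at the level of an improvement.

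A reader might infer that the key secondary endpoints amount to 29 tests with a 77% false positive risk. The documents do not support that. The key group gives at most 14 contrasts. The other 15 are IBDQ contrasts filed under other endpoints, and three of those concern a total score that SAP 2.2.2 does not list. Even 14 is an upper count, because the SAP speaks of estimating differences at each visit and does not define a separate test for each. Independence is also unrealistic for repeated visits of one marker.

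The objection does not remove the point. On the narrowest count of five, the rate is still 10% to 23% across the correlations examined. The lack of a defined test per visit also means that the deciding contrast for three endpoints is unspecified.

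**Conclusion.** The point holds as a limit on interpretation. With one test per key endpoint, the chance of at least one false positive under no effect is about 23% if independent, and 15% to 21% at assumed common correlations of 0.7 to 0.3. With all 14 key contrasts it is 51%, or 25% to 44% at the same correlations. The direction does not depend on the count or on the correlation assumed. Under the current text, a significant key secondary result is nominal, whether or not the primary succeeds.

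Two stronger readings should be resisted. One is that the primary type I error or the sample size is compromised. It is not, because there is a single primary test, and its power reproduces at 120 per group. The other is that the sponsor plans a confirmatory secondary claim. No section says so; the plan simply leaves the status of these results unstated. This is a cheap improvement and not the correction of an error.

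**What to change.** Before unblinding, take these steps.

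1. Reconcile the definition of clinical remission. SAP 9.3 requires a score of 0 for both rectal bleeding and stool frequency, whereas SAP 2.2.2 and Protocol 2.2 and 9.6.3 allow stool frequency of 0 or 1. Until this is settled, the endpoint cannot enter any sequence.
2. Replace the multiplicity sentence in SAP 9.1 with a sequence that opens only if the primary is significant at two-sided 0.05. Name one contrast per key endpoint: the Month 6 contrast, or the single test for time to relapse. The sponsor chooses the order, since nothing in the documents dictates one. Formal testing stops at the first non-significant result.
3. Report all other months, the overall effects and the IBDQ scores with nominal p-values labelled descriptive.

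If no secondary claim is intended, the minimum is to drop the word key and state that all secondary p-values are nominal and supportive.

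The cost is SAP wording plus the reconciliation in step 1. It needs no patients, no new data and no primary alpha, and the plan to have "approximately 260 subjects will be randomized" is unchanged. The SAP is dated 2 April 2018, and Protocol 3.1.3 expects the last visit in the second quarter of 2018. Protocol 5.5.1 withholds the randomization list until the database is declared clean, so the change is feasible if the blind is still intact. The downside is that results after the first failed step become descriptive, however small their p-values.
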